1.2 Primary Endpoints

- Complete responses (CRs) and partial responses (PRs) according to Response Evaluation Criteria in Solid Tumors (RECIST) version 1.1.
- Adverse events (AEs: clinical manifestations and laboratory tests) and serious adverse events (SAEs) according to the NCI Common Terminology Criteria for Adverse Events [CTCAE] version 5.0.

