Diarrhea	7 (53.8)	0 (0.0)
Nausea	8 (61.5)	0 (0.0)
Stomatitis	6 (46.2)	0 (0.0)
Metabolism and nutrition disorders	12 (92.3)	5 (38.5)
Hyperphosphatemia	12 (92.3)	4 (30.8)
Decreased appetite	3 (23.1)	0 (0.0)
Skin and subcutaneous tissue disorders	8 (61.5)	1 (7.7)
Dermatitis acneiform	3 (23.1)	0 (0.0)

A total of 7 patients (53.8%) experienced at least 1 event of Grade ≥ 3 regardless of relationship to futibatinib; PTs for which the incidence of Grade ≥ 3 events was at least 5% comprised only hyperphosphatemia.

A total of 5 patients (38.5%) experienced at least 1 treatment-related AE of Grade ≥ 3 . The most common of the treatment-related AE was hyperphosphatemia (n=4; 30.8%). Seven SAEs were reported for 6 patients (46.2%). Among them 3 SARs were assessed as either related to futibatinib and/or pembrolizumab in 3 patients, including 1 Grade 2 fatigue considered by the investigator to be related to futibatinib and considered by the company to be related to futibatinib and pembrolizumab in 1 patient, 1 event of Grade 3 rash considered to be related to pembrolizumab in 1 patient, and 1 event of Grade 3 Type 1 diabetes mellitus considered to be related to pembrolizumab in 1 patient.

In summary, the safety profile observed as of the cut-off date in this study for futibatinib 20mg QD in combination with pembrolizumab 200mg Q3W is largely consistent with the known safety profile for single agent futibatinib and pembrolizumab, respectively. There were no DLTs reported and beside hyperphosphatemia only few \geq Grade 3 TEAE observed. Enrollment of further patients at the futibatinib 20mg QD plus pembrolizumab 200mg Q3W dose level into the tumor type specific expansion part is currently ongoing.

Phase 2 Study Evaluating Futibatinib (TAS-120) Plus Pembrolizumab in the Treatment of Advanced or Metastatic Urothelial Carcinoma (Protocol TAS-120-203)

Study Design:

Study TAS-120-203 is an open-label, nonrandomized, multicenter Phase 2 study evaluating the combination of futibatinib and pembrolizumab in patients with advanced or metastatic urothelial carcinoma (UC) who are not candidates to receive a platinum-based treatment regimen.

The study will begin with a safety lead-in period. During this period, a total of 6 patients with advanced or metastatic UC will be enrolled and treated for at least one 21-day cycle. Patients will be enrolled into this initial safety lead-in period without regard for *FGFR* alteration status.

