6.2 Serious Adverse Events

Serious Adverse Events will be reported per standard IRB reporting requirements.

Serious Unexpected problems will be reported per standard IRB reporting requirements.

Assessment of Intensity

Maximum intensity should be assigned to an adverse experience. Intensity will be assigned a grade of 1-5. Final arbitration of intensity in cases of differing assessments by different practitioners will be the attending physician. Day to day fluctuations of intensity may not be recorded but rather the worst grade over the longest time period may be recorded.

Assessment of Seriousness

Definition of Serious Adverse Experience (SAE)

A serious adverse drug experience is any adverse experience occurring at any dose that results in any of the following outcomes:

Death: Is immediately life threatening (immediate risk of death from the reaction as it occurred). This does not include a reaction that, had it occurred in a more severe form, might have caused death. Death due to disease progression or relapse is not considered an SAE unless the investigator deems it possibly related to study drug. Death due to progression of disease will be reported per MD Anderson IRB standard guidelines.

Disability/Incapacitation

Results in persistent or significant disability/incapacity (permanent or substantial disruption of a person's ability to conduct normal life functions).

Congenital anomaly/birth defect

Important medical events that may not result in death, be life-threatening, or require hospitalization may be considered a serious adverse drug experience when, based upon appropriate medical judgment, they may jeopardize the patient and may require medical or surgical intervention to prevent one of the outcomes listed in this definition. Examples of such medical events include allergic bronchospasm requiring intensive treatment in an emergency room or at home, blood dyscrasias or convulsions that do not result in inpatient hospitalization, or the development of drug dependency or abuse.

Hospitalization

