In general, hospitalization signifies that the patient has been detained (usually involving at least an overnight stay) at the hospital or emergency ward for observation and/or treatment that would not have been appropriate in the physician's office or outpatient setting. When in doubt as to whether "hospitalization" occurred or was necessary, the adverse experience should be considered serious. Results in or prolongs an existing inpatient hospitalization. Hospitalization for elective surgery or routine clinical procedures** that are not the result of an adverse experience (e.g., elective surgery for a pre-existing condition) need not be considered adverse experiences and should be documented as appropriate. If anything untoward is reported during the procedure, that occurrence must be reported as an adverse experience, either 'serious' or 'non-serious' according to the usual criteria. New

hospitalization or prolonging of current hospitalization for disease progression or disease-related symptom management will not be considered a Serious Adverse Event.

****Routine Clinical Procedure:** one which is defined in the protocol as a procedure which may take place during the study period and should not interfere with the study drug administration or any of the ongoing protocol specific procedures.

SAE is any other important medical event that based upon appropriate medical judgement may jeopardize the patient or may require medical or surgical intervention to prevent one of the other outcomes listed in the definitions above. (e.g., may not result in death, be life-threatening, or require hospitalization).

The following are not considered hospitalizations for the purposes of assessing seriousness (however, one of the other serious criteria may apply):

- Hospitalizations for preplanned procedures;
- Hospitalization for study-related treatment and procedures.

Assessment of Causality

Every effort should be made by the investigator to explain clinically significant adverse experience and to assess its relationship, if any, to the study medication.

Immediate Reporting of Serious Adverse Experiences within 24 hours

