Serious adverse experiences (SAEs) which occur at any time after first dose of study drug or performance of protocol mandated research procedure and within 30 days after receiving the last dose of study drug(s) or prior to commencement of new therapy will be reported to the IRB per institutional standard policy. All SAEs should be documented in the patient's medical records or on the institutional standard forms (immediate reporting versus AE log).

All patients with serious adverse experiences should be followed until resolution, stabilization, death, or commencement of new therapy.

Instances of death, cancer, or congenital abnormality brought to the attention of the Investigator at any time after cessation of study medication and considered by the Investigator to be possibly related to study medication should be reported to the MD Anderson Cancer Center Institutional Review Board within 30 days.

Serious Adverse Event (SAE) Reporting Requirements for M D Anderson Sponsor Single Site IND Protocol

An adverse event or suspected adverse reaction is considered "serious" if, in the view of either the investigator or the sponsor, it results in any of the following outcomes:

- Death
- A life-threatening adverse event
- Inpatient hospitalization or prolongation of existing hospitalization
- A persistent or significant incapacity or substantial disruption of the ability to conduct normal life functions.
- A congenital anomaly/birth defect.

Note: grade 3 and 4 eye related toxicities will be reported as SAEs.

Important medical events that may not result in death, be life-threatening, or require hospitalization may be considered a serious adverse drug experience when, based upon appropriate medical judgment, they may jeopardize the patient or subject and may require medical or surgical intervention to prevent one of the outcomes listed in this definition. Examples of such medical events include allergic bronchospasm requiring intensive treatment in an emergency room or at home, blood dyscrasias or convulsions that do not result in inpatient hospitalization, or the development of drug dependency or drug abuse (21 CFR 312.32).

- Important medical events as defined above, may also be considered serious adverse events. Any important medical event can and should be reported as an SAE if deemed appropriate by the Principal Investigator or the IND Sponsor, IND Office.

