- All events occurring during the conduct of a protocol and meeting the definition of a SAE must be reported to the IRB in accordance with the timeframes and procedures outlined in “The University of Texas M. D. Anderson Cancer Center Institutional Review Board Policy on Reporting Adverse Events for Drugs and Devices”.
- Serious adverse events will be captured from the time of the first protocol-specific intervention, until 30 days after the last dose of drug, unless the participant withdraws consent.
- Serious adverse events must be followed until clinical recovery is complete and laboratory tests have returned to baseline, progression of the event has stabilized, or there has been acceptable resolution of the event.
- All SAEs, expected or unexpected/ initial or follow up, must be reported to the IND Office **within 5 working days of knowledge of the event** regardless of the attribution.
- Death or life-threatening events that are unexpected, possibly, probably or definitely related to drug must be reported (initial or follow up) to the IND Office **within 24 hours of knowledge of the event**
- Additionally, any serious adverse events that occur after the 30-day time period that are related to the study treatment must be reported to the IND Office. This may include the development of a secondary malignancy.
- The electronic SAE application (eSAE) will be utilized for safety reporting to the IND Office and MD Anderson IRB.
- All events reported to the supporting company must also be reported to the IND Office

Reporting to FDA:

- Serious adverse events will be forwarded to FDA by the IND Sponsor according to 21 CFR 312.32.

It is the responsibility of the PI and the research team to ensure serious adverse events are reported according to the Code of Federal Regulations, Good Clinical Practices, the protocol guidelines, the sponsor's guidelines, and Institutional Review Board policy.

Pregnancy

If a patient becomes pregnant while in the study, the study treatment must be immediately discontinued. Pregnancy information in a female patient (or for the female partner of a male patient) should be reported **as soon as possible** from the time the Investigator first becomes aware of a pregnancy or its outcome. This should be performed by completing a Pregnancy Form and faxing or e-mailing it to Taiho's Pharmacovigilance or designee. The eSAE application will be used to report pregnancy as "Other Important Medical Event" to the IND Office.

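### Section 6.2 holds two lists of seriousness criteria that classify an admission for disease-related symptoms differently, the end of SAE capture varies between sections, and no text says which governs the primary safety endpoint

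*Combined protocol and SAP*

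**What the plan says.** Section 1.2 makes AEs and SAEs, graded by CTCAE 5.0, a primary endpoint. Section 7.2 plans only a descriptive summary of toxicity by grade, type and dose level. It gives no SAE case definition, so Section 6.2 has to supply one.

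Section 6.2 contains two lists.

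- **List A**, under the assessment of seriousness. On deaths: "Death due to disease progression or relapse is not considered an SAE unless the investigator deems it possibly related to study drug". On admissions, new "hospitalization or prolonging of current hospitalization for disease progression or disease-related symptom management will not be considered a Serious Adverse Event". Hospitalization is described as being kept, usually at least overnight, "at the hospital or emergency ward for observation and/or treatment".
- **List B**, under the SAE reporting requirements for the institution's sponsor IND. It applies to an adverse event or suspected adverse reaction. It lists death, life-threatening events, "Inpatient hospitalization or prolongation of existing hospitalization", incapacity and congenital anomaly, with no disease-related exception. It adds: "Note: grade 3 and 4 eye related toxicities will be reported as SAEs".

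Three places state when collection or reporting ends.

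- Section 5.6 closes AE collection at 30 days after the last dose or at new antitumor therapy, whichever comes earlier. Related SAEs are collected through survival follow-up.
- Section 6.2, on reporting to the IRB, says within 30 days of the last dose or before new therapy starts.
- Section 6.2, in the IND requirements, says SAEs are captured "until 30 days after the last dose of drug, unless the participant withdraws consent". Later related SAEs still go to the IND Office.

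**The concern.** A primary endpoint needs one case definition. Here the same patient can be a case or not depending on which part of Section 6.2 the data manager applies. The List A exemption depends on a judgement that an admission is disease-related, made in an open-label single-arm trial. An admission exempted in this way may never be recorded as an SAE, and then the alternative count cannot be recovered later. Such admissions are foreseeable: the patients have advanced disease, and Section 7.3 allows treatment beyond RECIST progression. At stake is whether the reported SAE rate can be interpreted.

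**Working it through.** **1. Does the rule on progression close the gap?** Section 5.6 says progression of the cancer is not an AE. List B applies only to AEs or suspected reactions, so an admission or death that is purely progression largely falls outside List B as well as List A. Section 5.6 also says that a clinically significant deterioration of signs or symptoms already present is an AE. Take a patient admitted as an inpatient for worsening tumour pain, where the worsening is not simply recorded as progression:

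| Step | List A | List B |
|---|---|---|
| Is it an AE (Section 5.6)? | Yes | Yes |
| Inpatient admission? | Yes | Yes |
| Exception for disease-related symptoms? | Yes | None |
| SAE? | **No** | **Yes** |

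The conflict is real for this class of event.

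**2. Other differences.** List A includes the emergency ward. List B says inpatient and does not define it. This difference widens List A. The Grade 3-4 eye note widens List B.

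**3. End of capture.** Consider an unrelated SAE 20 days after the last dose, when new antitumor therapy has already begun. It is outside the Section 5.6 AE window, inside the IND window (if consent stands), and inside or outside the IRB wording depending on how its 'or' is read.

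**4. Size.** The only SAE rate for this combination in the documents is the phase 1b study in Section 2.4: seven SAEs in 6 of 13 patients. 6/13 = 46.2%, which reproduces the stated figure (exact 95% CI 19.2% to 74.9%). Three SAEs in 3 patients were related: 3/13 = 23.1% (5.0% to 53.8%). That leaves 6 − 3 = 3 patients with only unrelated SAEs.

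Assumption: List B would count all 6 patients, and k of those 3 had only disease-related admissions, which List A would drop. Rate under List A = (6 − k)/13; ratio of B to A = 6/(6 − k); expected cases in 24 patients = 24 × (6 − k)/13.

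| k | Rate under List A | Ratio B/A | Cases in 24 |
|---|---|---|---|
| 0 | 46.2% | 1.0 | 11.1 |
| 1 | 38.5% | 1.2 | 9.2 |
| 2 | 30.8% | 1.5 | 7.4 |
| 3 | 23.1% | 2.0 | 5.5 |

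Section 2.4 does not say which k applies.

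**5. Decision rules.** The stopping rule in Sections 7.1 and 7.3 counts DLTs, and the efficacy rule counts responses (at least 3 of 12, then at least 7 of 24). Table 11 reproduces from exact binomial sums (4.87% at a response rate of 15%, 86.20% at 40%). None of this uses SAEs.

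**The case against.** The strongest defence is that the two lists can be read together. List B never defines hospitalization, so List A may be meant to supply the definition. List A itself also speaks of inpatient stays and resolves doubt toward serious. The differing windows may reflect separate channels, the IRB and the IND Office. Section 5.6 also lets day-to-day fluctuations of the disease go unrecorded unless they are clinically significant, worse than baseline and possibly drug-related.

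Part of this stands. The emergency-ward difference is one of clarity, and separate channels are a plausible explanation. But the protocol does not say that List A qualifies List B, or which channel feeds the endpoint. An admission for clinically significant worsening is also more than a day-to-day fluctuation.

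A reader might draw four stronger conclusions that the documents do not support.

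- *The SAE rate differs two-fold.* That equates not drug-related with disease-related. Section 2.4 gives no causes for the four unrelated SAEs and does not state that study's SAE definition, which may already exclude disease-related admissions. A ratio of 2.0 is the extreme of an assumed range.
- *Progression deaths are counted under one list only.* Section 5.6 keeps pure progression largely out of both.
- *The eye note contradicts List A.* Nothing in List A denies it; it adds a category.
- *The exemption would make the regimen look better tolerated than the approved one.* The tolerability rationale rests on 70% dose interruptions. The documents give no SAE rate for that comparator.

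**Conclusion.** The point holds for two matters: admissions for worsening disease-related symptoms, and the end of SAE capture. For both, the protocol gives different answers and does not say which one defines the primary endpoint. Whether an emergency-ward stay counts as hospitalization also needs one statement.

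The size is unknown. The ratio of 1.0 to 2.0 by patient is a sensitivity range from 13 patients in another study. It rests on the assumption in the working and ignores the emergency-ward and eye-event differences, which act in opposite directions. Type I error, power, sample size and both stopping rules are unchanged. The consequence is confined to the descriptive SAE result, but that result is a named primary endpoint, so the wording should be settled.

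**What to change.** 1. State in Section 1.2 or 7.2 which SAE definition governs the endpoint. The List B criteria, with the Grade 3-4 eye note, would serve.
2. State once whether an overnight emergency-ward stay counts as hospitalization.
3. Set one capture window that reconciles Section 5.6 with the two texts in Section 6.2. It should say whether new antitumor therapy closes capture of unrelated SAEs, and how long related SAEs are collected. If IRB and IND reporting need other windows, label them as reporting rules only.
4. Replace the List A exemption for disease-related symptom management with an instruction to record these hospitalizations as SAEs with a flag. Report the SAE rate with and without the flagged events.
5. Leave in force the Section 5.6 rule that progression is not an AE, and list progression deaths separately.

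The cost is protocol wording, a few more SAE forms, one extra table row and possibly a higher headline SAE rate. The flag keeps both counts available.

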6.3 Statement of Good Clinical Practices

This trial will be conducted in adherence to the study protocol, Good Clinical Practices as defined in Title 21 of the US Code of Federal Regulations Parts 50, 54 56, 312 and Part 11 as well as ICH GCP consolidated guidelines (E6) and applicable regulatory requirements.
<http://www.fda.gov/cder/guidance/index.htm>

Destruction of the expired/unused investigational product will be performed per the MDACC policy. NCCN/Taiho will be informed prior to destruction of the investigational product.

6.4 Data Collection

All patients who meet eligibility criteria and are enrolled in this trial will be registered in Clinical Oncology Research Database at MD Anderson Cancer Center.

Data Protection and Confidentiality

All patients who meet eligibility criteria and are enrolled in this trial will be registered in Clinical Oncology Research e-Database (CORe) [or other similar e-Database](#) at the University of Texas MD Anderson Cancer Center at Houston. All protocol participants must be registered in the CORe. The date in the current informed consent document is displayed to ensure only the most current IRB approved version is used. Consent date, registration date, off study date, and evaluability data are required for all registrants.

Consent date, registration date, off study date, and evaluability data are required for all registrants. Consent date, registration date, off study date, and evaluability data are required for all registrants. Molecular and Clinical Data Integrated Platform (MOCLIA) will be used as the electronic case report form for this protocol and adverse events and protocol specific data will be entered into MOCLIA. Concurrent medications will be computed on the medical record of the patient in EPIC and not recorded on the case reporting form.

The principal investigator agrees to keep all information and results concerning the study confidential. The confidentiality obligation applies to all personnel involved with this clinical trial. The Investigator must ensure that each participant's anonymity will be maintained in accordance with applicable laws. The principal investigator should keep a separate log of ID numbers, names and medical record numbers. This information will be located in MOCLIA and EPIC. Documents that contain the names associated with these ID numbers (e.g., written consent/assent forms) should be maintained by the Investigator in strict confidence (MOCLIA and EPIC) except to the extent necessary to allow auditing by regulatory authorities, auditing or monitoring by the IRB.

The Principal Investigator shall obtain all such permissions and authorizations as may be necessary or desirable to allow the collection and use of information protected under federal privacy laws and state privacy laws, including permission/authorization for monitoring and analysis (including re-analysis in combination with results of other studies), for regulatory submission purposes and for applicable reporting (if any).

6.5 Investigator Reporting Responsibilities

The conduct of the study will comply with all FDA safety reporting requirements.

IND Annual Reports (DSUR)

If the FDA has granted an IND number, it is a requirement of 21 CFR 312.33, that an annual report is provided to the FDA within 60-days of the IND anniversary date. 21 CFR 312.33 provides the data elements that are to be submitted in the report.

TAIHO and/or partner shall be responsible for the preparation, content and submission of a Development Safety Update Report (DSUR). TAIHO may delegate the preparation of the DSUR to a third party. If requested, TAIHO shall provide the Investigator with the final version of this report within 15 calendar days after submission to health agencies and ethics committees.

All adverse experience reports must include the patient number, age, sex, weight, severity of reaction (mild, moderate, severe), relationship to drug (probably related, unknown relationship, definitely not related), date and time of administration of test medications and all concomitant medications, and medical treatment provided. The investigator is responsible for evaluating all adverse events to determine whether criteria for "serious" and as defined above are present.

The Annual Report should be filed in the study's Regulatory Binder.

